5. INTRODUCTION

5.1. Background of Duchenne Muscular Dystrophy

Duchenne muscular dystrophy (DMD) is a rare (estimated incidence of 1 in 3,500 to 5,000 live male births; CDC 2009; Emery 1991), degenerative, X-linked recessive genetic disorder caused by mutations in the dystrophin gene. In DMD, mutations in the dystrophin gene disrupt the open reading frame, resulting in an absence of functional dystrophin, a critically important part of the protein complex that connects the cytoskeletal actin of a muscle fiber to the extracellular matrix. In the absence of dystrophin, the stress of repeated muscle contraction causes cellular degeneration, regeneration, and inflammation, and, over time, myonecrosis.

The progression of DMD follows a highly predictable course. Significant motor deficits may be present during the first year of life, but diagnosis is usually made between the ages of 3 to 5 years when toddlers begin to show functional symptoms (e.g., waddling gait, toe walking, and difficulty climbing stairs). Over time, ambulation becomes increasingly abnormal, and by 8 years of age, most patients lose the ability to rise from the floor and climb stairs, and often fall while walking. By 10 to 14 years of age, most lose the ability to walk. Upper limb, cardiac, and diaphragmatic muscles progressively weaken during adolescence. Historically, patients died from respiratory or cardiac failure in their late teens or early 20s (Brooke 1989, Eagle 2002). Recent research suggests that use of ventilation support and steroids may increase life span by several years; however, DMD still has a mortality rate of 100% (Kohler 2009).

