11.4. Recording Adverse Events

All AEs/SAEs experienced from the time of informed consent/assent to the last follow-up will be recorded within each patient's CRF. Information should include: a concise description of the event; date and time of event onset and resolution; determination of seriousness, severity, corrective treatment, outcome, and relationship to IP or study procedure or underlying disease; and any action taken will be recorded. Resolution occurs when the patient has returned to his baseline state of health or further improvement or worsening of the event is not expected.

Whenever possible, a diagnosis will be recorded as an AE, rather than symptoms or isolated laboratory abnormalities related to that diagnosis. Several symptoms or laboratory results that are related to the same diagnosis can thus be part of the same AE. A medical or surgical procedure is not an AE; rather the condition leading to the procedure should be recorded as the AE. Similarly, death is not an AE, but is rather the outcome of the AE(s) that resulted in death. If the AE(s) leading to death are not known, then death must be reported as an AE. All AEs will be followed until the resolution of AE, completion of the patient's study participation, or study termination, whichever occurs first. SAEs will be followed until resolution or until the condition stabilizes or returns to baseline status.

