5.5.7.1. Adverse Events

Adverse events will be mapped to MedDRA v17.1 preferred terms (PT) and system organ classifications (SOC). Multiple occurrences of the same AE (at the PT level) in the same subject will be counted only once in the frequency tables. All adverse event tables will be summarized by Baseline ambulatory status and overall. If a subject experiences multiple episodes of the same event with a different relationship/severity, the event with the strongest relationship or maximum severity to the study drug will be used to summarize the AEs by relationship and severity.

Only treatment-emergent adverse events (TEAEs) will be summarized. Non-emergent events will be included in the subject listings. TEAEs and treatment-related TEAEs will be summarized by SOC, PT, and severity. Additionally, serious AEs (SAEs), regardless of their treatment-emergent status, will be summarized by SOC and PT. The following listings will be produced:

- 1) All AEs
- 2) Moderate and Severe AEs
- 3) Treatment-Related AEs
- 4) SAEs

5) AEs leading to discontinuation

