5.5.7.1.1. Adverse Events of Special Interest

Summaries of TEAEs of special interest (AESIs) and other AEs of Interest will be summarized by SOC and PT. All SMQs listed below will include broad and narrow terms. The AESIs are:

- Hypersensitivity (Anaphylactic Reaction SMQ and Anaphylactic/Anaphylactoid Shock Conditions SMQ)
- Renal Toxicity (Acute Renal Failure SMQ)
- Leukopenia and Neutropenia (Haematopoietic SMQ)
- Infusion Site Reactions (Extravasation Events SMQ and the following PTs: Application Site Erythema, Application Site Rash, Catheter Site Haematoma, Catheter Site Haemorrhage, Catheter Site Related Reaction, Infusion Site Rash, Infusion Site Swelling)
- Severe Cutaneous Adverse Reactions (Severe Cutaneous Adverse Reactions SMQ)
- Infusion Related Reactions (PTs of Nausea, Vomiting, Pyrexia, Body
 Temperature Increased, Erythema, Flushing Infusion Related Reaction,
 Hypotension, Blood Pressure Decreased, Diastolic Hypotension, Orthostatic
 Hypotension, Procedural Hypotension, Blood Pressure Ambulatory Decreased,
 Blood Pressure Diastolic Decreased, Blood Pressure Orthostatic Decreased, Blood
 Pressure Systolic Decreased, Blood Pressure Systolic Inspiratory Decreased)
- Drug Induced Hepatotoxicities (Cholestasis and Jaundice of Hepatic Origin SMQ, Hepatic Failure, Fibrosis and Cirrhosis and Other Liver Damage-Related Conditions SMQ, Hepatitis, Non-infectious SMQ, Liver Neoplasms, Benign (incl Cysts and Polyps) SMQ, Liver Malignant Tumours SMQ, Liver Tumours of Unspecified Malignancy SMQ, Liver Related Investigations, Signs and Symptoms SMQ, Liver-Related Coagulation and Bleeding Disturbances SMQ)
- Cardiac Events (Cardiomyopathy SMQ, Cardiac Failure SMQ, and Arrhythmia Related Investigations, Signs and Symptoms SMQ)
- Coagulopathy (Haemorrhage Terms (excluding lab terms) SMQ, Haemotopoietic Thrombocytopenia SMQ, PTs in the Embolism and Thrombosis High Level Group Terms (HLGT)

The Other AEs of Interest are:

 Port-Related Events⁺ (Embolic and Thrombotic Events, Venous SMQ, Extravasation Events (Injections, Infusions and Implants) SMQ, PTs in the following High Level Terms (HLTs): Sepsis, Viraemia and Fungaemia NEC, Implant and Catheter Site Reactions, PTs in the following HLGTs: Endocardial Disorders and Device Issues. In addition, a search will be performed on the verbatim terms for "port", "central venous" and "central line")

- Fractures (PTs in the following HLGTs: Fractures and Bone and Joint Injuries)

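### The Cardiac Events AESI names no query for diagnosed rhythm or conduction disorders, so its table and listing may miss them

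*SAP*

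**What the plan says.** SAP 5.5.7.1.1 defines each adverse event of special interest by a set of MedDRA queries or terms. The cardiac entry reads "Cardiac Events (Cardiomyopathy SMQ, Cardiac Failure SMQ, and Arrhythmia Related Investigations, Signs and Symptoms SMQ". The only part of it that names arrhythmia is "Arrhythmia Related Investigations, Signs and Symptoms SMQ". A general rule stands above the list: "All SMQs listed below will include broad and narrow terms". A listing accompanies each AESI table.

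The hepatic entry in the same section contains the parallel query "Liver Related Investigations, Signs and Symptoms SMQ" and seven other SMQs. Most of these are named for diseases, for example "Hepatitis, Non-infectious SMQ".

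Protocol 11.4 tells sites how to record events: "Whenever possible, a diagnosis will be recorded as an AE, rather than symptoms or isolated laboratory abnormalities related to that diagnosis". On coding, SAP 5.5.7.1 states "Adverse events will be mapped to MedDRA v17.1 preferred terms (PT" and the system organ classes. Neither document reproduces the terms inside any SMQ.

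**The concern.** Judged by title, the one query in Cardiac Events that names arrhythmia looks for tests, signs and symptoms. Under Protocol 11.4, an event recorded well at the site should arrive as a diagnosis. If the search is built around findings and the data around diagnoses, a recorded rhythm or conduction disorder could be coded to a term that none of the three SMQs contains.

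What is at stake is the completeness of one grouped count. Safety is the primary objective, and the Cardiac Events table is the planned output that gathers cardiac AEs across preferred terms. A reader who takes its top line as the number of patients with a cardiac event would read too low a figure if diagnosed arrhythmias sit outside it.

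**Working it through.** The plan states no figure on this point, so there is none to reproduce. The check sets the relevant sections side by side.

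**1. What the cardiac search contains by name.** There are three SMQs. Two are named for diseases (cardiomyopathy, cardiac failure). The third is the only one that names arrhythmia, and it is an investigations, signs and symptoms query. No arrhythmia diagnosis query is listed, nor any preferred terms or higher-level groupings for rhythm or conduction.

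**2. What the broad-and-narrow rule does.** It takes each listed SMQ at full width. It does not bring in an SMQ that is not listed.

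**3. How the SAP treats comparable cases.**

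| AESI or AE of interest | How the search is completed |
|---|---|
| Hepatic | Investigations query plus seven other SMQs, most named for diseases |
| Infusion site reactions | SMQ plus named preferred terms |
| Coagulopathy | SMQs plus terms from a high-level group |
| Port-related events | SMQs, terms from higher-level groupings, and a verbatim search |
| Cardiac, for arrhythmia | Investigations query only |

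For the liver, the SAP does not rely on the investigations query alone. Elsewhere it adds terms to the SMQs. For arrhythmia it does neither and gives no reason.

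**4. How events will be recorded.** Protocol 11.4 prefers a diagnosis over its symptoms or isolated laboratory findings. Protocol 11.2.1 makes a test abnormality an AE when it alters medical care, and ECG is among its examples. A rhythm disorder found on ECG or Holter and acted upon could thus enter as an AE, preferably under its diagnosis.

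**5. Where else such an event would be seen.**
- SAP 5.5.7.1: TEAE tables by SOC, PT and severity; SAEs by SOC and PT whether or not treatment-emergent; a listing of all AEs.
- SAP 5.5.7.4: a 12-lead ECG shift table, and markedly abnormal criteria for QTcF, PR and QRS, the last including conduction disturbance. Heart rate has limits of normal. There is no rhythm-diagnosis category.
- SAP 5.5.7.6 and Section 6: Holter data, scheduled at Screening, Week 48 and Week 96, are listed and not summarised.

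The event therefore stays in the report. What it may not enter is the Cardiac Events table and its listing.

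**6. Scale.** Inputs: planned enrolment N of about 20 (SAP 5.1), and SAP 5.4.8, which takes percentages over the number of subjects in the analysis population. If k patients have no cardiac event other than a missed one, the grouped incidence falls by 100 × k/N percentage points. For k = 1 and N = 20, this is 100 × 1/20 = 5.0. A patient who also has an event caught by one of the three SMQs is already counted, and the fall is then zero.

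**The case against.** The strongest reply is that the deciding fact lies outside the documents. Whether a diagnosed arrhythmia is missed depends on the v17.1 contents of three SMQs, and none is shown. Broad terms of the Cardiomyopathy or Cardiac Failure SMQ may already include some rhythm or conduction diagnoses. This stands. It limits the conclusion to a possibility and makes the dictionary check part of the fix.

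A second reply is that the hepatic comparison is imperfect. The cardiac AESI also has two disease queries beside its investigations query, AESIs in this section differ in breadth (renal toxicity is one SMQ), and nothing commits the SAP to covering every arrhythmia diagnosis. This stands in part. Different breadth is not a contradiction. But the two cardiac disease queries are not named for arrhythmia, and the SAP evidently meant arrhythmia to be covered, since it lists a query for it.

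A third reply is that no event is lost. With about 20 patients the SOC and PT tables can be read in full, the AESI tables are descriptive with no test or decision attached, and the protocol's endpoint is the incidence of all AEs. This stands, and it keeps the point small.

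A reader might also infer that the plan leaves uncovered the cardiac risk described in Protocol 5.1: "Historically, patients died from respiratory or cardiac failure in their late teens or early 20s". The documents do not support that. The sentence concerns cardiac failure, which has its own SMQ in the AESI, and it does not mention arrhythmia.

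**Conclusion.** The point holds as a possible gap in one grouped safety output. By name, the Cardiac Events search reaches arrhythmia only through an investigations, signs and symptoms query, while the protocol directs sites to record diagnoses. Diagnosed rhythm or conduction disorders may therefore be missing from the cardiac AESI table and its listing.

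The size is about 5 percentage points of grouped cardiac incidence for each patient whose only cardiac event is missed. This assumes about 20 treated patients. It is a scale per patient; the documents give no arrhythmia rate from which to expect a number of such patients.

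Two stronger readings are tempting and are not supported. One is that arrhythmias will be missed: without the v17.1 term lists, only "may" is justified. The other is that arrhythmias would vanish from the cardiac safety results: they remain in the general TEAE tables, in the SAE table where serious, and in the AE listings, and the overall AE incidence is unaffected.

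**What to change.** Before database lock, take the combined term list of the three current SMQs, broad and narrow, and check it against MedDRA v17.1 for diagnosed rhythm and conduction disorders. Then add to Cardiac Events either the arrhythmia diagnosis query or queries, or an explicit list of preferred terms for these disorders. Keep the three current SMQs.

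Choose the added terms from the dictionary and not from the events already reported. The study is open-label, and a list fitted to known events would be harder to defend.

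The cost is about one line in the SAP, one dictionary check, and a slightly broader term list to review. Data collection and patient procedures do not change.

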10.3.3. Clinical Laboratory Evaluations

The following routine clinical laboratory tests will be collected at the time points specified in Section 2 and analyzed by an accredited central laboratory selected by the Sponsor and prepared according to the Laboratory Manual provided for the study:

Chemistry: Sodium, chloride, potassium, calcium, glucose, creatinine, blood urea

nitrogen (BUN), albumin, uric acid, total bilirubin, alkaline phosphatase, amylase, alanine aminotransferase (ALT), aspartate aminotransferase (AST), gamma-glutamyl transferase (GGT), lactase dehydrogenase (LDH), C-reactive protein (CRP), creatine kinase

(CK), and serum cystatin C

Hematology: Red blood cells (RBCs), total white blood cells (WBCs), hemoglobin,

hematocrit, neutrophils, lymphocytes, monocytes, eosinophils,

basophils, platelets, and abnormal cells

Coagulation Screen: Prothrombin time, International Normalized Ratio (INR), and

activated partial thromboplastin time (aPTT)

Urinalysis: pH, specific gravity, protein, glucose, ketones, cytology, hemoglobin,

and kidney injury molecule-1 (KIM-1)

Any value outside of the current reference ranges for the laboratory performing the test will be flagged on the laboratory results. The Investigator will determine whether abnormal assessment results are clinically significant (CS) or not clinically significant (NCS). Clinical significance is defined as any variation in assessment results that has medical relevance resulting in an alteration in medical care. If clinically significant deterioration from baseline levels is noted, the Investigator will continue to monitor the patient with additional assessments until:

- Values have reached normal range and/or baseline levels; or
- In the judgment of the Investigator together with the Sponsor's Medical Monitor, abnormal values assessed to be not related to the administration of investigational

product or other protocol-specific procedures, and additional assessments are not medically indicated.

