11.2. Definition of Adverse Events

11.2.1. Adverse Event (AE)

An AE is any untoward medical occurrence in a clinical trial participant, which does not necessarily have a causal relationship with the investigational drug. An AE can, therefore, be any unfavorable and unintended symptom, sign, disease, condition, or test abnormality that occurs during or after administration of an IP whether or not considered related to the IP. Adverse events include:

- Symptoms described by the patient or signs observed by the Investigator or medical staff.
- Test abnormalities (laboratory tests, ECG, X-rays, etc.) that result in an alteration in medical care (diagnostic or therapeutic).

Abnormalities present at baseline are considered AEs only if they reoccur after resolution or worsen during the AE collection period.

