5.5.7.2. Laboratory Measurements

Descriptive statistics for continuous hematology, clinical chemistry, urinalysis, and coagulation laboratory measurements will be presented by time point. Summary statistics for each lab parameter and time point as well as the change from Baseline to the time point will be displayed. For each numeric laboratory parameter, box plots of values over time will be generated. A shift table will compare N (%) of low, normal, and high status of the lab values at Baseline to their worst value post-Baseline through Week 96. A table summarizing the frequency and percent of subjects meeting the predefined markedly abnormal criteria at each visit will be presented. The predefined markedly abnormal criteria are defined below in Tables 3-1, 3-2, and 3-3. All laboratory values will be displayed in a data listing.

Table 3-1 Predefined Markedly Abnormal Hematology Laboratory Values

Test	Unit	Markedly Abnormal Criteria
Hematocrit	1	< LLN
Hemoglobin	g/L (or mmol/L)	< LLN
Red blood cell count	T/L	< LLN
White blood cell count	count/L	$>1.5 \times ULN \text{ or } < LLN$
Platelet count	10^3/L	< 150 or < 200 with a decrease of at least 100
Basophils (abs)	count/L	> ULN or < LLN
Eosinophils (abs)	count/L	> 1.5xULN or < LLN
Lymphocytes (abs)	count/L	< LLN
Monocytes (abs)	count/L	< LLN
Neutrophils (abs)	count/L	>1.5 × ULN or < 1000

ULN = upper limit of normal

LLN = lower limit of normal

abs = absolute

Table 3-2 Predefined Markedly Abnormal Chemistry Laboratory Values

		Predefined	Change	
Test	Unit	Decrease	Increase	Markedly Abnormal Criteria
Fasting blood glucose*	mmol/L	3.1	3.2	
Urea (BUN)	mmol/L			Value >1.5 × Baseline Value AND > ULN
Creatinine	μmol/L		35	Value >1.5 × ULN
Sodium	mmol/L	8	8	
Potassium	mmol/L	1.1	1.0	Value >5.5 mmol/L or < 3 mmol/L
Chloride	mmol/L	9	8	
Uric acid	μmol/L			>1 × ULN
Calcium#	mmol/L	0.30	0.30	
Total cholesterol	mmol/L		1.73	
AST (SGOT)	U/L			Value ≥3 × Baseline Value
ALT (SGPT)	U/L			Value ≥2 × Baseline Value
Gamma GT (GGT)	U/L			Value >3 × Baseline Value OR > ULN
Alkaline phosphatase	U/L			Value >1.5 × ULN
Total protein@	g/L	11	10	
Albumin	g/dL	1 g/dL decrease or	1 g/dL increase	Value < LLN or > ULN
Total bilirubin ^{&}	μmol/L		10	Value >1.5 × ULN
LDH	U/L			Value ≥2 × Baseline Value
Creatine phosphokinase	U/L			Value ≥2 × Baseline Value
Triglycerides	mmol/L	_	2.88	
Cystatin C	mg/L			>ULN

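### The Coagulopathy AESI names no clotting-test or coagulation-disorder terms, and none of prothrombin time, INR or aPTT has a markedly-abnormal criterion

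*SAP*

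**What the plan says.** The SAP (5.5.7.1.1) opens the definition of this AESI with "Coagulopathy (Haemorrhage Terms (excluding lab terms) SMQ", then adds a thrombocytopenia query and the preferred terms grouped under embolism and thrombosis. It adds that every standardised query is run with both broad and narrow terms. A different AESI, Drug Induced Hepatotoxicities, includes "Liver-Related Coagulation and Bleeding Disturbances SMQ".

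The protocol (10.3.3) collects a coagulation panel with the other safety laboratory tests: "Prothrombin time, International Normalized Ratio (INR") and "activated partial thromboplastin time (aPTT"). Protocol 11.2.1 counts as adverse events "Test abnormalities (laboratory tests, ECG, X-rays, etc.) that result in an alteration in medical care (diagnostic or therapeutic").

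For laboratory values, SAP 5.5.7.2 plans descriptive statistics by time point, change from Baseline, box plots, a listing, and a low/normal/high shift from Baseline to the worst value through Week 96. It also plans a per-visit table of patients who meet preset limits: "The predefined markedly abnormal criteria are defined below in Tables 3-1, 3-2, and 3-3". Those three tables cover hematology, chemistry and urinalysis.

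**The concern.** A reader of the study report will take the Coagulopathy line as the summary of clotting risk. As specified, it summarises bleeding, low platelets and thrombosis. An AE that consists of a deranged clotting test, or of a diagnosed clotting disorder without a bleed, is arguably the most literal case of coagulopathy, yet no component names it. If the liver query picked it up, it would appear under hepatotoxicity.

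The laboratory section would be the natural second place to look, but its markedly-abnormal table has no coagulation rows. The incidence of laboratory abnormalities is a stated safety endpoint (Protocol 7.3.1), so a whole collected panel without a preset abnormality criterion weakens the reporting of that endpoint.

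**Working it through.** The documents give no figure to reproduce. The check is a comparison of definitions.

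**1. AESI components against clotting-test terms (SAP 5.5.7.1.1)**

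| Component | Names clotting-test or coagulation-disorder terms? |
|---|---|
| Haemorrhage query | No; laboratory terms expressly excluded |
| Thrombocytopenia query | No; concerns platelets |
| Embolism and thrombosis group terms | No; concerns clots |

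Result: 0 of 3 components. The exclusion of laboratory terms is attached to the haemorrhage query only. The other two miss clotting tests by subject, not by exclusion.

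**2. Collected tests against markedly-abnormal rows**

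| Test (Protocol 10.3.3) | Table 3-1 | Table 3-2 | Table 3-3 |
|---|---|---|---|
| Prothrombin time | none | none | none |
| INR | none | none | none |
| aPTT | none | none | none |

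The tables hold 10 + 20 + 2 = 32 rows. Result: 0 of 3 coagulation tests appear. By contrast, Table 3-2 has rules for total cholesterol, triglycerides and total protein, which are not in the protocol's chemistry panel. Platelets have both an AESI query and a Table 3-1 rule.

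**3. What remains for coagulation values**

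- Through Week 96: descriptive statistics, change from Baseline, box plots, the shift table and the listing.
- After Week 96: safety laboratory samples are scheduled at Weeks 120 and 144 (Protocol Table 3, SAP Table 2). The shift table has stopped by then. The markedly-abnormal table runs at each visit but omits coagulation. Only descriptive statistics, box plots and the listing are left, so there is no categorical summary.

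**4. What remains for an AE**

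A treatment-emergent prolonged aPTT appears in the TEAE tables by system organ class, preferred term and severity, and in the listing of all AEs (SAP 5.5.7.1).

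**5. Scale**

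With about 20 patients (SAP 5.1), one patient is 1/20 = 5 percentage points of AESI incidence. This shows what one case would weigh; it does not estimate how many there will be.

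**The case against.** The strongest reply is that the plan makes a coherent separation: clinical bleeding, thrombosis and thrombocytopenia go to the AESI, and test values go to the laboratory section. Several points support this.

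- Protocol 13.8.2.3 promises abnormal-value frequency tables only for selected parameters, so no commitment is broken. Coagulation is not the only omission: amylase and C-reactive protein are collected and also have no row in Table 3-2.
- Many markedly-abnormal rules are just below LLN or above ULN (hemoglobin, uric acid, cystatin C and others). For rules of that kind, the shift table already gives coagulation a similar worst-value count through Week 96.
- Protocol 11.4 prefers a diagnosis to an isolated laboratory finding, so a bare laboratory term may seldom be the recorded AE.
- The adverse drug reactions listed in Protocol 5.3 include no coagulation or bleeding event.

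Much of this stands, and it limits the point to a coverage gap. It does not remove it. The separation is not applied consistently: the hepatotoxicity and cardiac AESIs include investigation-type queries, the infusion-reaction AESI includes blood pressure and temperature terms, and Coagulopathy alone excludes laboratory terms, with no reason given. Recording a diagnosis does not help either, because no Coagulopathy component names a coagulation disorder. Coagulation is also the only complete panel without a rule.

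A reader might infer more than this: that such events vanish from the report, that the whole AESI excludes laboratory terms, or that clotting-test AEs contribute exactly zero to it. The first is wrong, because the TEAE tables and listings retain them. The second is wrong, because the exclusion qualifies one query. The third cannot be shown, because the documents do not list the contents of the queries.

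**Conclusion.** The point holds as a coverage gap in the SAP. A clotting-test AE or a diagnosed coagulation disorder would probably not be counted as Coagulopathy, and 0 of 3 coagulation tests has a markedly-abnormal criterion. The per-visit abnormality table therefore leaves out the panel, and nothing categorical covers its Week 120 and 144 results.

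Two assumptions matter. Which preferred terms each query contains is read from its name. That includes the suggestion that the liver-related query might pick up an INR event. The number of such events is not given and may be none; an accompanying bleed, thrombosis or low platelet count would still be counted through its own component.

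This is not a contradiction of the protocol and it puts no hypothesis test at risk, since the safety analyses are descriptive. It is worth correcting because the category's label promises more than its contents, and the correction needs no new data.

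**What to change.** 1. Add to the Coagulopathy AESI an explicit list of preferred terms for prolonged prothrombin time, raised INR, prolonged aPTT and diagnosed coagulation disorders. A written list avoids relying on query contents.
2. Within the AESI, show bleeding, thrombosis, thrombocytopenia and clotting-test events on separate lines, so that the wider search does not blur the clinical events. Place diagnosed coagulation disorders on a stated line.
3. Add a separate coagulation table of markedly-abnormal criteria with rows for all three tests, and include it in the per-visit summary through Week 144. A multiple of ULN is one option; 1.5 x ULN, which the SAP uses for creatinine, alkaline phosphatase and bilirubin, is an example and not a justified limit for clotting tests. The sponsor should set the cut-off before database lock.
4. If the omission is intended, say so in the SAP and give the reason.

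The cost is SAP wording, a slightly longer search list and one more table. The AESI count may be slightly higher. No extra samples, visits or patients are needed.

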- Falls (search of verbatim terms for "fall")
- + For subjects who have a port, Port-Related Events will only be identified after the port insertion occurred.

A corresponding listing will be generated for each table.

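### The Falls table selects events only by searching verbatim text for 'fall', so it can miss true falls and admit non-falls

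*SAP*

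**What the plan says.** SAP 5.5.7.1.1 names a set of adverse events of special interest and, separately, three Other AEs of Interest: port-related events, fractures and falls. The whole definition of the third is "Falls (search of verbatim terms for" followed by the one word 'fall'. Neither the SAP nor the protocol gives another way into the Falls table.

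The two neighbouring categories are built differently:

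- Fractures are taken from coded terms: "Fractures (PTs in the following HLGTs: Fractures and Bone and Joint Injuries".
- Port-related events start from coded groupings (SMQs, HLTs and HLGTs), and three verbatim strings are then searched in addition.

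Coded terms exist for every event. SAP 5.5.7.1 states: "Adverse events will be mapped to MedDRA v17.1 preferred terms (PT) and system organ classifications (SOC". Once the events are selected, "Summaries of TEAEs of special interest (AESIs) and other AEs of Interest will be summarized by SOC and PT". For the listings, the SAP says "A corresponding listing will be generated for each table", so the Falls listing holds what the Falls table holds.

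**The concern.** In the port-related category the verbatim search adds to the coding. In the falls category it is the only selection rule. A literal search for four letters depends on how each site happens to word its report. The past tense 'fell' does not contain the string, while phrases that have nothing to do with falling over can contain it. Neither error is caught, because no review of the hits is planned.

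The sponsor chose to report falls next to fractures in a population in which falling is expected: Protocol 5.1 describes frequent falls as walking deteriorates. If the Falls table is read as the number of patients who fell, it may give the wrong number. The Falls listing would not reveal this, since it is drawn from the same selected events.

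**Working it through.** The documents state no count or rate of falls, so there is no figure to reproduce. Three checks apply.

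**1. What the rule selects.** A case-insensitive substring test for 'fall' was run on invented example verbatims. The documents contain no real ones.

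| Example verbatim | Selected? | Comment |
|---|---|---|
| Fall; Falls; Accidental fall | Yes | Correct |
| Bruise from falling | Yes | Correct, even if coded to the injury |
| Fell; Fell from wheelchair; Tripped and fell | No | True falls missed |
| Tripped; Slipped in bathroom | No | May or may not be falls |
| Ankle fracture | No | Cause not stated |
| Fall in blood pressure; Fall allergies | Yes | Not falls |

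Both kinds of error therefore follow from the rule as written.

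**2. Effect of one misclassified patient.** SAP 5.1 plans about 20 patients. SAP 5.5.7.1 presents all adverse event tables overall and by baseline ambulatory status.

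- Overall: 1/20 = 5 percentage points, down for a patient with falls of whom no report matches, up for a patient without a fall whose unrelated text matches.
- Within a subgroup: 1/10 = 10 points if it has 10 patients, 1/5 = 20 points if it has 5. The documents give no subgroup sizes, so these are assumptions.

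**3. Illustration of missed patients.** Let F be the number of patients with at least one fall, k the fall reports per patient, and s the share of fall reports that lack the string. If the wording of each report is independent, a patient is missed only when all k reports lack it, so

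expected patients missed = F × s^k, and reported share = (F − F × s^k)/20.

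F, k and s are all assumed. With F = 8, the true share is 8/20 = 40%:

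| k | s = 10% | s = 30% | s = 50% |
|---|---|---|---|
| 1 | 0.8 missed, 36% reported | 2.4 missed, 28% reported | 4.0 missed, 20% reported |
| 2 | 0.08 missed, 39.6% reported | 0.72 missed, 36.4% reported | 2.0 missed, 30% reported |
| 3 | 0.01 missed, 40.0% reported | 0.22 missed, 38.9% reported | 1.0 missed, 35% reported |

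With eight reports in all, the chance that at least one lacks the string is 1 − (1 − s)^8: 57%, 94% and 99.6% for the three values of s.

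Two cautions apply. If a site always uses the same wording, reports within a patient are not independent, and repeated falls protect less than the table suggests. The table also leaves out false inclusions, which push the count the other way.

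**The case against.** **No evidence of an actual error.** A reader might infer that falls are undercounted. The documents do not support that. They show no verbatim terms and no counts, and if every site writes 'fall' nothing is missed. False matches also mean that the net error could be upward. This objection stands in full: the rule can misclassify, but neither the size nor the net direction is known.

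**The verbatim search has a purpose.** Protocol 11.4 says: "Whenever possible, a diagnosis will be recorded as an AE, rather than symptoms or isolated laboratory abnormalities related to that diagnosis". An injury caused by a fall may therefore be coded to the injury, and a definition by coded term alone would lose it. A reader might also infer that any difference between the Falls table and the main preferred-term table is a mistake. It is not, because a Falls category that is wider than one preferred term is legitimate. This stands as a reason to keep the search. It does not justify using the search alone, since the port-related category combines both routes.

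**Nothing is lost from the report.** All treatment-emergent events enter the tables by system organ class, preferred term and severity, and SAP 5.5.7.1 provides a listing of all adverse events. Protocol 13.8.2.1 also plans a listing of all treatment-emergent events. With about 20 patients, a careful reader could find falls that the search missed. This stands and limits the consequence to one supplementary table and its listing.

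**Little depends on the count.** Falls is not one of the adverse events of special interest, the safety analysis is descriptive with a single treatment group, and no test or decision in the documents uses the number. This also stands.

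**Further strings bring noise.** 'Tripped' or 'slipped' alone need not mean a fall. This is correct, and it is why those strings are optional and need the hits to be reviewed.

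**Conclusion.** The point holds as a minor one. As written, the Falls definition can omit patients who fell and include patients who did not, so the count may be wrong in either direction. Each misclassified patient moves the overall percentage by 5 points with about 20 patients, and by more within an ambulatory-status subgroup. How many patients would be affected cannot be derived from the documents. The illustration runs from almost none to 4 of 8 patients missed, depending wholly on assumed values, and the error is zero if sites always write 'fall' and no unrelated text matches.

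The conclusion assumes that the search is carried out literally, as an automated string match without clinical judgement. The SAP describes nothing more. It does not extend to the overall safety evaluation, because the events remain in the main tables and the full listing.

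**What to change.** Replace the Falls line in SAP 5.5.7.1.1 with a definition in three parts:

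1. Events coded to the MedDRA term or terms for fall, named from the dictionary version that the SAP already uses (17.1).
2. In addition, events whose verbatim text contains 'fall' or 'fell', with 'tripped' and 'slipped' as optional further strings. Keeping the verbatim search retains injuries that are described as due to a fall but coded to the injury.
3. Review of all hits before database lock to remove non-falls, with the decisions documented.

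This brings Falls into line with the port-related category. It costs one line in the SAP and a small amount of review work at this sample size, and needs no new data.
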